5.7.3 Use in Pregnancy

If a subject inadvertently becomes pregnant while on treatment with pembrolizumab, the subject will immediately discontinue treatment. The site will contact the subject at least monthly and document the subject's status until the pregnancy has been completed or terminated.

5.7.4 Use in Nursing Women

It is unknown whether pembrolizumab is excreted in human milk. Since many drugs are excreted in human milk, and because of the potential for serious adverse reactions in the nursing infant, subjects who are breast-feeding are not eligible for enrollment.

5.8 Criteria for Subject Withdrawal/Discontinuation from Study

Subjects may withdraw consent at any time for any reason or be dropped from the trial at the discretion of the investigator should any untoward effect occur. In addition, a subject may be withdrawn by the investigator or the IND Office if enrollment into the trial is inappropriate, the trial plan is violated, or for administrative and/or other safety reasons. Specific details regarding discontinuation or withdrawal are provided below.

A subject must be discontinued from the trial for any of the following reasons:

 The subject or legal representative (such as a parent or legal guardian) withdraws consent.

- Investigator's decision to withdraw the subject
- Administrative reasons

5.8.1 Discontinuation of Study Therapy

Subjects must discontinue therapy for the following reasons:

- Withdrawal / discontinuation from study.
- Worsening oral lesions requiring discontinuation from study therapy, in the opinion of the treating physician
- Unacceptable adverse experiences as described in Section 5.2.1.2
- Intercurrent illness that prevents further administration of treatment
- Investigator's or patient's decision
- The subject has a confirmed positive serum pregnancy test
- Development of oral cancer
- The subject is lost to follow-up

For patients that develop oral cancer during the study or for patients that are lost to follow up, only the procedures described under "Lon-Term Follow-Up" in section 6.0 will be performed.

If possible, subjects that discontinue therapy before completing 4 cycles of treatment should remain on study and continue to undergo study procedures and follow-ups as described in Section 6.0.

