5.2.1.2 Dose Modification

Adverse events (both non-serious and serious) associated with pembrolizumab exposure may represent an immunologic etiology. These adverse events may occur shortly after the first dose or several months after the last dose of treatment. Pembrolizumab must be withheld for drug-related toxicities and severe or life-threatening AEs as per Table 3 below. See Section 5.6.1 and Events of Clinical Interest Guidance Document for supportive care guidelines, including use of corticosteroids.

Table 3

Dose Modification Guidelines for Drug-Related Adverse Events

Toxicity	Hold Treatment For Grade	Timing for Restarting Treatment	Discontinue Subject
Diarrhea/Colitis	2-3	Toxicity resolves to Grade 0-1.	Toxicity does not resolve within 12 weeks of last dose or inability to reduce corticosteroid to 10 mg or less of prednisone or equivalent per day within 12 weeks.
	4	Permanently discontinue	Permanently discontinue
AST, ALT, or	2	Toxicity resolves to Grade 0-1	Toxicity does not resolve within 12 weeks of last dose.
Increased Bilirubin	3-4	Permanently discontinue (see exception below) ¹	Permanently discontinue
Type 1 diabetes mellitus (if new onset) or	T1DM or 3-4	Hold pembrolizumab for new onset Type 1 diabetes mellitus or Grade 3-4 hyperglycemia associated with evidence of	Resume pembrolizumab when patients are clinically and metabolically stable.

NCT02882282

Toxicity	Hold Treatment For Grade	Timing for Restarting Treatment	Discontinue Subject							
Hyperglycemia		beta cell failure.								
Hypophysitis	2-3	Toxicity resolves to Grade 0-1	Toxicity does not resolve within 12 weeks of last dose or inability to reduce corticosteroid to 10 mg or less of prednisone or equivalent per day within 12 weeks.							
	4	Permanently discontinue	Permanently discontinue							
Hyperthyroidism	3	Toxicity resolves to Grade 0-1	Toxicity does not resolve within 12 weeks of last dose or inability to reduce corticosteroid to 10 mg or less of prednisone or equivalent per day within 12 weeks.							
	4	Permanently discontinue	Permanently discontinue							
Hypothyroidism	2-4	Therapy with pembrolizumab can be continued while treatment for the thyroid disorder is instituted	Therapy with pembrolizumab can be continued while treatment for the thyroid disorder is instituted.							
Infusion Reaction	3-4	Permanently discontinue	Permanently discontinue							

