6.1 TRIAL FLOW CHART

6.2 Study Flow Chart

Trial Period:	Screening Phase		reatment Follow-Up Cycles ^a									Long-Term Follow-Up			
Treatment Cycle/Title:	Pre- screening (Visit 1)	Main Study Screening (Visit 2)	1	2	3	4	End of Treatment / Re-evaluation	Post-treatment			As needed for trial data interpretation				
Scheduling Window (Days):		-28 to -1 days	1	W (± 7	eek days) ^b	Month 3 $\pm 7 \text{ days}^{c}$		(± 1	nth) (± 2 months)		s) 36	throughout and after the study period as determined by the Principal Investigator		
Administrative Procedures			_				,	_							
Informed Consent	X		Г	l	l		Ι	Г			Ι				I
LOH evaluation	X														
Tobacco and alcohol use history	X						X	X	X	X	X	X	X	X	
Prior oral cancer history	X														
Inclusion/Exclusion Criteria		X													
Demographics and Medical History		X													
Concomitant Medication Review		X													
Trial Treatment Administration			X	X	X	X									
Oral Cancer-free Survival Status															X
Clinical Procedures/Assessi	nents														•
Review Adverse Events		X		X	X	X	Xa								1
Physical Examination		X		X	X	X	X ^a X	X	X	X	X	X	X	X	1
ECOG Performance Status		X													
Laboratory Procedures/Ass	sessments: an	alysis perfo	rmed	l by l	LOC	AL la	boratory				•				
Pregnancy Test – Urine or Serum �-HCG		Xª					Xª								
Urinalysis		X					X ^a								
CBC with Differential		X		X	X	X	X	Xa		X					
Comprehensive Serum Chemistry Panel		X		X	X	X	X	Xa		X					
T3, FT4 and TSH		X					X ^a	Xª							
Non-invasive Efficacy Meas	surements						_								
Oral lesion measurement		X					X			X					
Tumor Biopsies/Archival T				4 30										 	 

Trial Period:	Screening Phase		Treatment Cycles ^a				Follow-Up							Long-Term Follow-Up	
Treatment Cycle/Title:	Fitle: Prescreening (Visit 1)		1	2	3	4	End of Treatment / Re-evaluation	Pos			ost-tro	eatme	nt	As needed for trial data interpretation	
Scheduling Window (Days):		-28 to -1 days	1	W (± 7 d	eek days 7) ^b	Month 3 ± 7 days ^c	(± 1 month)		month) (± 2 months)				s) 36	throughout and after the study period as determined by the Principal Investigator
Archival or Newly Obtained Tissue Collection ^d	X														
Newly Obtained Tissue Collection		Xe					X			X					
Correlative Studies Blood Collection ^f	X			X			X			X				X	
Oral Swab Collection ^f	X			X			X			X				X	

^a To be performed only in subjects randomized to the experimental arm. Pregnancy test must be performed <72 hours prior to the first dose of study medication.

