7.1.1.8 Oral Cancer-Free Survival Status

Information on time to development of oral cancer/disease progression/recurrence, sites of disease, development of second primary tumors, additional therapy, long-term survival, and other relevant clinical data may be obtained throughout and after the study period as deemed necessary by the Principal Investigator for trial data interpretation. Patients (or their family members or designees) may be contacted by telephone or in writing or by electronic mail or during clinic visits during or after treatment discontinuation for collection of oral cancersurvival status. The information may also be obtained through chart reviews.

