7.1.2.1 Adverse Event (AE) Monitoring

7.1.2 Clinical Procedures/Assessments

The investigator or qualified designee will be responsible for assigning attribution of adverse events to the study drug. The investigator or qualified designee will assess each subject to evaluate for potential new or worsening AEs as specified in the Trial Flow Chart and more frequently if clinically indicated. Adverse experiences will be graded and recorded according to NCI CTCAE Version 4.0 (see Section 7.2)Toxicities will be characterized in terms regarding seriousness, causality, toxicity grading, and action taken with regard to trial treatment.

For subjects receiving treatment with pembrolizumab AEs of unknown etiology associated with pembrolizumab exposure should be evaluated to determine if it is possibly an event of clinical interest (ECI) of a potentially immunologic etiology (termed immune-related adverse events, or irAEs); see the separate ECI guidance document in the Appendix regarding the identification, evaluation and management of potential irAEs.

Please refer to section 7.2 for detailed information regarding the assessment and recording of AEs.

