For the purpose of this study, adverse events that in the opinion of the treating investigator are related to planned procedures (e.g., usual pain, usual bleeding, intra- or post-procedure electrolyte imbalances and other clinically insignificant laboratory abnormalities) will not be captured and/or reported.

Adverse events will only be recorded for patients that undergo randomization. Adverse events will be recorded from the time the patient is randomized through the end of treatment / reevaluation visit (month 3) or 90 days following cessation of treatment, whichever is longer.

Any new serious adverse event that occurs more than 30 days after last study drug administration should be reported if considered related to study drug (e.g., secondary cancer). Should a patient discontinue from or complete the study and commence subsequent anticancer therapy within 30 days of the last study drug administration, adverse events attributable to this subsequent therapy should not be recorded.

Laboratory abnormalities are usually not recorded as adverse events; however, signs and/or symptoms that are associated with laboratory findings requiring study withdrawal, dose modification, or medical intervention (e.g., anemia requiring transfusions or hyperglycemia requiring treatment) or other abnormal assessments (e.g., ECG, radiographs, vital signs) must be recorded as adverse events (or serious adverse events) if they meet the definition of an adverse event (or serious adverse event). In addition, laboratory abnormalities marked as clinically significant should also be recorded as adverse events. The investigator will report the most severe grade of the clinically significant laboratory abnormality and will evaluate its relationship to the study drug and clinical condition.

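### Section 5.8.1 moves patients with oral cancer to long-term follow-up before the plan's own adverse event window closes, so scheduled safety assessment depends on the primary outcome

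*Combined protocol and SAP*

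**What the plan says.** All places are in the combined protocol and SAP.

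- **Section 5.8.1** lists "Development of oral cancer" among the reasons for stopping therapy. It then says: "For patients that develop oral cancer during the study or for patients that are lost to follow up, only the procedures described under" the Long-Term Follow-Up heading of Section 6.0 are to be performed. The next sentence asks that subjects who stop before four cycles, if possible, "should remain on study and continue to undergo study procedures and follow-ups as described in Section 6.0".
- **Section 6.2, flow chart.** The one row legibly marked under Long-Term Follow-Up is "Oral Cancer-free Survival Status". Adverse event review, physical examination, blood count, chemistry and thyroid tests are marked only in earlier columns. The table came through text extraction partly broken.
- **Section 7.1.1.8** describes that one procedure as status information that "may be obtained throughout and after the study period as deemed necessary by the Principal Investigator for trial data interpretation". It does not name adverse events.
- **Section 7.1.2.1** ties routine assessment to the chart: the person responsible "will assess each subject to evaluate for potential new or worsening AEs as specified in the Trial Flow Chart and more frequently if clinically indicated".
- **Section 7.2.1** has adverse events recorded in randomized patients from randomization to the month 3 visit "or 90 days following cessation of treatment, whichever is longer". It makes no exception for oral cancer.
- **Section 7.3.1** runs serious event reporting to 90 days after treatment or the start of new anti-cancer therapy, whichever is earlier. Events of clinical interest run to 90 days, or to 30 days after new anti-cancer therapy starts, whichever is earlier. Diagnosis of oral cancer ends neither.
- **Section 8.3** includes every treated patient in the toxicity analysis.

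**The concern.** Oral cancer is a component of the primary endpoint. If its diagnosis also ends scheduled safety assessment, how completely adverse events are ascertained depends on the efficacy outcome. A treated patient with the event is observed less closely than one without it, yet both count in the same toxicity table.

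Timing adds weight. Of adverse events linked to pembrolizumab, Section 5.2.1.2 says: "These adverse events may occur shortly after the first dose or several months after the last dose of treatment". Section 4.2.4 describes oral cancer treatment as surgery, often followed by radiation or chemoradiation. Drug-related events in these patients would be harder to detect and attribute if no assessment were scheduled.

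Section 5.8.1 also conflicts with itself. A patient diagnosed before the fourth dose falls under the sentence that restricts procedures and under the sentence that asks for them to continue.

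**Working it through.** **Text.** Take a pembrolizumab patient diagnosed at week 5. The first rule in Section 5.8.1 leaves only survival status, so the month 3 adverse event review and laboratory tests are not scheduled. The next sentence in 5.8.1 asks for them to continue if possible. Section 7.2.1 still requires recording through month 3 at least. These cannot all be followed as written.

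Now take a patient diagnosed from the month 3 biopsy. The adverse event review scheduled for that visit is already due, so what goes is the later laboratory and thyroid tests. The month headings of those columns are not fully legible, so it cannot be said how many fall inside the window.

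**Inputs for the size** (Section 8.2 unless noted)
- Prior-cancer stratum: 56 patients; hazard per year 0.1179 (control), 0.053 (treatment).
- IEN-alone stratum: 48 patients; hazard per year 0.0813 (control), 0.0366 (treatment).
- At 1:1 allocation, 28 + 24 = 52 in the pembrolizumab arm (equal split within strata assumed).
- Four doses three weeks apart (Section 5.2): the last is on day 63, so the window ends on day 63 + 90 = 153. This assumes no delay and a first dose at randomization.

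**Check of the plan's figures.** The control hazards follow from the two-year rates: −ln(0.79)/2 = 0.1179 and −ln(0.85)/2 = 0.0813. Multiplied by 0.45 they give 0.0531 and 0.0366. A 10,000-replicate simulation of the stratified log-rank test, with the stated boundaries, uniform accrual (assumed) and 10% loss, gave 79.1% power against the stated 79%. At a hazard ratio of 0.4 it gave 85.6% against 88%, which may reflect accrual and loss details not given and does not bear on this point.

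**Expected diagnoses in the pembrolizumab arm by time t (years)**

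N(t) = 28(1 − exp(−h₁t)) + 24(1 − exp(−h₂t))

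At day 153, t = 153/365.25 = 0.419:
- treatment hazards: 28 × 0.02196 + 24 × 0.01521 = 0.98
- control hazards (no drug effect): 28 × 0.04819 + 24 × 0.03348 = 2.15

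| Time | Treatment hazards | Control hazards |
|---|---|---|
| Month 3 (day 91) | 0.59 | 1.29 |
| Day 153 | 0.98 (1.9% of 52) | 2.15 (4.1% of 52) |
| Day 195 (assumed 6-week delay) | 1.25 | 2.73 |

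The chance of at least one such patient by day 153 is 1 − exp(−(28h₁ + 24h₂)t): 63% under treatment hazards, 89% under control hazards.

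**Effect on the toxicity table.** For illustration, apply the 9.5% Grade 3-5 incidence that Section 4.2.4 quotes from lung cancer patients, equally to all 52: 0.095 × 52 = 4.9 patients with such an event. The affected patients would contribute 0.095 × 0.98 = 0.09 to 0.095 × 2.15 = 0.20 of these. If every one were missed, the expected observed rate would fall from 9.5% to 9.5 × (1 − 0.0188) = 9.3%, or to 9.5 × (1 − 0.0414) = 9.1%. That is an upper bound under this assumption, because events before diagnosis and those caught by serious event reporting would still appear.

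**The case against.** The strongest reply is that Section 5.8.1 governs scheduled procedures and lifts no recording or reporting duty. That is right. Section 7.2.1 recording has no exception, and 7.3.1 reporting applies to any subject. Serious events must be followed to outcome, and related serious events are reportable even outside the window. Section 7.1.2.1 allows more frequent assessment if clinically indicated, the opening text of Trial Procedures allows unscheduled procedures, and flow chart footnote f allows extra blood and swabs at cancer diagnosis. Section 7.1.1.8 allows contact at clinic visits and chart review.

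A reader might therefore infer too much: that 5.8.1 ends all visits, tests and adverse event review, or that immune events in these patients would not be looked for. The documents do not support that. What is lost is the protocol-scheduled assessment, and ascertainment then rests on unscheduled contact, clinical care and chart review.

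A reader might also infer that adverse event review stops only for patients with the primary event. The flow chart shows no legible adverse event review after month 3 for anyone, although the Section 7.2.1 window runs to about day 153. From month 3 on, the visible difference between patients with and without oral cancer is in examinations and laboratory tests. The gap between chart and window is thus partly general, though the broken table makes this less certain.

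Finally, the sentence about stopping before four cycles may keep an early case on full procedures. It says only if possible and does not say which sentence prevails, so it shows the ambiguity without settling it. None of these replies reconciles the sections.

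**Conclusion.** The conflict is real and lies in the current text: Section 5.8.1 with the flow chart on one side, and Sections 7.2.1 and 7.3.1 and the next sentence of 5.8.1 on the other. Followed literally, the first rule removes scheduled laboratory tests, and for diagnoses before month 3 the scheduled adverse event review, from patients because they had the primary event.

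The size is small: about 1.0 to 2.2 of 52 pembrolizumab patients inside the window, 0.6 to 1.3 of them before month 3. At least one case is more likely than not, but the toxicity rates would hardly move. This rests on constant hazards as the plan assumes, a 28/24 split, no dose delays, and the legible part of the flow chart. Diagnoses clustering at the month 3 biopsy would shift the counts by an amount the documents do not allow to be estimated. The case for correction is the consistency and completeness of the safety data; a material bias has not been shown.

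**What to change.** - In Section 5.8.1, state that the switch to Long-Term Follow-Up does not end adverse event data collection before the Section 7.2.1 window closes, and say how this fits with the sentence on stopping before four cycles.
- Record the start date of any new anti-cancer therapy, since the Section 7.3.1 windows depend on it.
- Reconcile the flow chart with the Section 7.2.1 window for all treated patients, for example by a footnote, because no adverse event review is legible after month 3.

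This concerns data collection only. Care and clinical monitoring after a cancer diagnosis are for the sponsor and investigators to settle when they reconcile the sections.

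The cost is one sentence, one footnote and one date field, plus a few extra data-collection contacts for about 1 to 2 patients, co-ordinated with their cancer care. Aligning the chart for all treated patients may add one adverse event contact each near the end of the window, if the chart as issued has none there.

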5.9 Subject Replacement Strategy

Efficacy analysis on this trial will be per intent-to-treat. As such, there will be no replacement for subjects that are randomized, but do not initiate and/or complete study procedures and treatments.

5.10 Clinical Criteria for Early Trial Termination

Early trial termination will be the result of the criteria specified below:

1. Quality or quantity of data recording is inaccurate or incomplete

- 2. Poor adherence to protocol and regulatory requirements
- 3. Incidence or severity of adverse drug reaction in this or other studies indicates a potential health hazard to subjects
- 4. Plans to modify or discontinue the development of the study drug

In the event of Merck decision to no longer supply study drug, ample notification will be provided so that appropriate adjustments to subject treatment can be made.

6.1 TRIAL FLOW CHART

6.2 Study Flow Chart

Trial Period:	Screening Phase		reatment Follow-Up Cycles ^a									Long-Term Follow-Up			
Treatment Cycle/Title:	Pre- screening (Visit 1)	Main Study Screening (Visit 2)	1	2	3	4	End of Treatment / Re-evaluation	Post-treatment			As needed for trial data interpretation				
Scheduling Window (Days):		-28 to -1 days	1	W (± 7	eek days) ^b	Month 3 $\pm 7 \text{ days}^{c}$		(± 1	nth) (± 2 months)		s) 36	throughout and after the study period as determined by the Principal Investigator		
Administrative Procedures			_				,	_							
Informed Consent	X		Г	l	l		Ι	Г			Ι				I
LOH evaluation	X														
Tobacco and alcohol use history	X						X	X	X	X	X	X	X	X	
Prior oral cancer history	X														
Inclusion/Exclusion Criteria		X													
Demographics and Medical History		X													
Concomitant Medication Review		X													
Trial Treatment Administration			X	X	X	X									
Oral Cancer-free Survival Status															X
Clinical Procedures/Assessi	nents														•
Review Adverse Events		X		X	X	X	Xa								1
Physical Examination		X		X	X	X	X ^a X	X	X	X	X	X	X	X	1
ECOG Performance Status		X													
Laboratory Procedures/Ass	sessments: an	alysis perfo	rmed	l by l	LOC	AL la	boratory				•				
Pregnancy Test – Urine or Serum �-HCG		Xª					Xª								
Urinalysis		X					X ^a								
CBC with Differential		X		X	X	X	X	Xa		X					
Comprehensive Serum Chemistry Panel		X		X	X	X	X	Xa		X					
T3, FT4 and TSH		X					X ^a	Xª							
Non-invasive Efficacy Meas	surements						_								
Oral lesion measurement		X					X			X					
Tumor Biopsies/Archival T				4 30										 	 

Trial Period:	Screening Phase		Treatment Cycles ^a				Follow-Up							Long-Term Follow-Up	
Treatment Cycle/Title:	Fitle: Prescreening (Visit 1)		1	2	3	4	End of Treatment / Re-evaluation	Pos			ost-tro	eatme	nt	As needed for trial data interpretation	
Scheduling Window (Days):		-28 to -1 days	1	W (± 7 d	eek days 7) ^b	Month 3 ± 7 days ^c	(± 1 month)		month) (± 2 months)				s) 36	throughout and after the study period as determined by the Principal Investigator
Archival or Newly Obtained Tissue Collection ^d	X														
Newly Obtained Tissue Collection		Xe					X			X					
Correlative Studies Blood Collection ^f	X			X			X			X				X	
Oral Swab Collection ^f	X			X			X			X				X	

^a To be performed only in subjects randomized to the experimental arm. Pregnancy test must be performed <72 hours prior to the first dose of study medication.

^b If there are treatment delays, timing of subsequent cycles will be adjusted so that pembrolizumab is given every 3 weeks (± 7 days)

^c In subjects who had a treatment delay, evaluation should be postponed until at least 2 weeks after last dose of treatment

^d At any time point after enrollment, any archival or newly obtained tissue as part of standard of care for monitoring of oral IEN or newly developed oral cancer may be collected for correlative studies. This applies to any subject participating in the study from the time of enrollment, regardless of LOH or randomization status.

^e During the screening phase, newly obtained tissue collection may be performed within 12 months before randomization

^f For patients diagnosed with oral cancer during the study, extra blood collection and oral swabs collection may be performed approximately at the time of diagnosis of invasive cancer.

NCT02882282

